7.1.6.2. Incomplete Dates

If an AE onset date is incomplete or completely missing, the following rules will be used to define treatment-emergent AE during the double-blind and open-label phases:

Events with Missing Onset Day and/or Month

The event is treatment-emergent during the double-blind phase if the following criteria are met:

- The month and year (or year) of onset date is the same as or after the month and year (or year) of the first dose of the blinded study drug, and
- For those who discontinued the blinded study drug permanently only: the month and year (or year) of onset date is the same as or before the month and year (or year) of the date of the last dose of the blinded study drug, and
- End date is as follows:
 - The (complete) end date is on or after the first dose date of the blinded study drug, or
 - The month and year (or year) of end date is the same or after the month and year (or year) of the first dose of the blinded study drug, or
 - End date is completely missing

The event is treatment-emergent during the open-label phase if the following criteria are met:

- The month and year (or year) of onset date is the same as or after the month and year (or year) of the first dose of the open-label study drug, and
- For those who discontinued the open-label study drug permanently only: the month and year (or year) of onset date is the same as or before the month and year (or year) of the date of the last dose of the open-label study drug, and
- End date is as follows:
 - The (complete) end date is on or after the first dose date of the open-label study drug, or
 - The month and year (or year) of end date is the same or after the month and year (or year) of the first dose of the open-label study drug, or
 - End date is completely missing

Events with Completely Missing Onset Date

An AE with a completely missing onset date is defined as treatment-emergent AE during the double-blind phase if end date is as follows:

- The (complete) end date is on or after the first dose date of the blinded study drug, or
- The month and year (or year) of end date is the same or after the month and year (or year) of the first dose of the blinded study drug, or
- End date is completely missing

An AE with a completely missing onset date is defined as treatment-emergent AE during the open-label phase if end date is as follows:

- The (complete) end date is on or after the first dose date of the open-label study drug, or
- The month and year (or year) of end date is the same or after the month and year (or year) of the first dose of the open-label study drug, or
- End date is completely missing

7.1.7. Summaries of AEs and Deaths

A brief summary of AEs (ie, the number and percentage of subjects) will be presented by treatment group for the following: (1) any treatment-emergent AE, (2) any Grade 3 or 4 treatment-emergent AE, (3) any Grade 2, 3 or 4 treatment-emergent AE, (4) any treatment-emergent study drug-related AE, (5) any Grade 3 or 4 treatment-emergent study drug-related AE, (6) any Grade 2, 3 or 4 treatment-emergent study drug-related AE, (7) any treatment-emergent serious adverse event (SAE), (8) any treatment-emergent study drug-related SAE,

- (9) any treatment-emergent AE leading to premature study drug discontinuation,
- (10) any treatment-emergent AE leading to dose modification or study drug interruption, and
- (11) any treatment-emergent death.

Treatment-emergent death refers to death that occurs between the first dose date and the last dose date (inclusive).

Summaries (number and percentage of subjects) of AEs (by SOC, HLT [if specified below], and PT) will be provided by treatment group and overall using the Safety Analysis Set as follows:

- All treatment-emergent AEs summarized by SOC, HLT, and PT
- Any Grade 3 or 4 treatment-emergent AEs
- Any Grade 2, 3, or 4 treatment-emergent AEs
- All treatment-emergent nonserious AEs occurring in at least 5% of subjects in any treatment group (this summary is generated per requirement for reporting in ClinicalTrials.gov)
- All treatment-emergent study drug-related AE summarized by SOC, HLT, and PT
- Any Grade 3 or 4 treatment-emergent study drug-related AEs
- Any Grade 2, 3, or 4 treatment-emergent study drug-related AEs
- All treatment-emergent SAEs
- All treatment-emergent study drug-related SAEs
- All treatment-emergent AEs leading to premature discontinuation from study drug
- All treatment-emergent AEs leading to dose modification or study drug interruption

Multiple events will be counted once only per subject in each summary. For data presentation, SOC (and HLT) will be ordered alphabetically, with PT sorted by decreasing total frequency. For summaries by severity grade, the most severe event will be selected.

In addition to the by-treatment summaries, data listings will be provided for the following:

- All AEs
- Grade 3 and 4 AEs
- SAEs

- Study drug-related SAEs
- Deaths
- AEs leading to premature discontinuation of study drug
- AEs leading to dose modification or study drug interruption

7.1.8. Potential Uveitis Events

Analysis will be performed to detect AEs where the symptoms reported may potentially represent uveitis. The list of PTs for potential uveitis events were defined by selecting eye disorder PTs based on MedDRA 19.1, which will be reviewed and edited by an external ophthalmologist for comprehensiveness.

A summary (number and percentage of subjects) of treatment-emergent potential uveitis events by PT will be provided by treatment group based on the Safety Analysis Set. A data listing of potential uveitis events will be provided.

7.1.9. Potential Cardiovascular Events

Potential cardiovascular events are defined as events with predefined list of MedDRA PTs based on 3 MedDRA SMQs: Ischemic central nervous system vascular conditions, Other ischemic heart disease, and Myocardial infarction, which was provided by Gilead Drug Safety and Public Health representative and reviewed by Gilead medical monitors.

A summary (number and percentage of subjects) of potential treatment-emergent cardiovascular events and serious cardiovascular events by PT will be provided by treatment group based on the Safety Analysis Set. A data listing of potential cardiovascular events will be provided.

7.2. Laboratory Evaluations

Summaries of laboratory data will be provided for the Safety Analysis Set. Analysis will be based on values reported in conventional units.

7.2.1. Summaries of Numeric Laboratory Results

Descriptive statistics (sample size, mean, SD, median, Q1, Q3, minimum, and maximum) will be provided by treatment group for each laboratory test specified in the study protocol as follows:

- Baseline values
- Values at each postbaseline analysis window
- Change from baseline to each postbaseline analysis window
- Percentage change from baseline to each postbaseline analysis window (if specified)

In the case of multiple values in an analysis window, data will be selected for analysis as described in Section 3.7.3.

Median (Q1, Q3) change from baseline in selected safety endpoints including the fasting lipid panel parameters, and fasting glucose over time will be plotted.

Metabolic Assessments

For the lipid panel and glucose measurements, only those under fasting status will be summarized.

Fasting lipid data (including total cholesterol, LDL, HDL and triglycerides) will also be analyzed using the following National Cholesterol Education Program (NCEP) Adult Treatment Panel (ATP) III categories {National Cholesterol Education Program (NCEP) 2001}:

- For total cholesterol (mg/dL): < 200 (desirable), 200-239 (borderline high), and ≥ 240 (high)
- For LDL (mg/dL): < 100 (optimal), 100-129 (near optimal/above optimal), 130-159 (borderline high), 160-189 (high), and ≥ 190 (very high)
- For HDL (mg/dL): < 40 (low), 40-59 (normal), and ≥ 60 (high)
- For triglycerides (mg/dL): < 150 (normal), 150-199 (borderline high), 200-499 (high), and ≥ 500 (very high)

The number and proportion of subjects for the above categories of each lipid parameter will be summarized by its baseline category for each treatment group at each visit.

In addition, the number and proportion of subjects who took lipid modifying medications at the study entry and initiated the medications will be provided, respectively.

A lipid modifying medication is defined as a medication with drug class = “LIPID MODIFYING AGENTS” and CMDECOD containing the wording of “STATIN”.

A sensitivity analysis of fasting lipid tests (including total cholesterol, LDL, HDL, triglycerides, and total cholesterol to HDL ratio) will be performed by excluding subjects who took lipid modifying medications at study entry or initiated the medications: baseline, postbaseline, and changes from baseline at Weeks 48 and 96 will be summarized. Only subjects with both baseline and postbaseline values (at Weeks 48 and 96 respectively) will be included in the analysis.

Calcium Corrected for Albumin

Calcium corrected for albumin will be calculated and summarized. The following formula will be used when both serum calcium and albumin results for a given blood draw are available and serum albumin value is < 4.0 g/dL.

Calcium corrected for albumin (mg/dL) = serum calcium (mg/dL) + $0.8 \times (4.0 - \text{albumin (g/dL)})$.

When albumin value is ≥ 4.0 g/dL, the actual calcium results will be used. Toxicity grading for calcium will be applied based on the corrected values.

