46.14	Chemistry: Summary of Indirect Bilirubin (mg/dL) by Visit	Safety Analysis Set
46.15	Chemistry: Summary of GGT (U/L) by Visit	Safety Analysis Set

Table Number	Title	Analysis Set
46.16	Chemistry: Summary of LDH (U/L) by Visit	Safety Analysis Set
46.17	Chemistry: Summary of Blood Urea Nitrogen (BUN, mg/dL) by Visit	Safety Analysis Set
46.18	Chemistry: Summary of Uric Acid (mg/dL) by Visit	Safety Analysis Set
46.19	Chemistry: Summary of Albumin (g/dL) by Visit	Safety Analysis Set
46.20	Chemistry: Summary of Creatine Kinase (U/L) by Visit	Safety Analysis Set
46.21	Chemistry: Summary of Total Protein (g/dL) by Visit	Safety Analysis Set
47.1.1	Metabolic Assessments: Summary of Fasting Total Cholesterol (mg/dL) by Visit	Safety Analysis Set
47.1.2	Metabolic Assessments: Shift Table of Fasting Total Cholesterol (mg/dL) by Visit	Safety Analysis Set
47.2.1	Metabolic Assessments: Summary of Fasting Direct LDL (mg/dL) by Visit	Safety Analysis Set
47.2.2	Metabolic Assessments: Shift Table of Fasting Direct LDL (mg/dL) by Visit	Safety Analysis Set
47.3.1	Metabolic Assessments: Summary of Fasting HDL (mg/dL) by Visit	Safety Analysis Set
47.3.2	Metabolic Assessments: Shift Table of Fasting HDL (mg/dL) by Visit	Safety Analysis Set
47.4	Metabolic Assessments: Summary of Fasting Total Cholesterol to HDL Ratio by Visit	Safety Analysis Set
47.5.1	Metabolic Assessments: Summary of Fasting Triglycerides (mg/dL) by Visit	Safety Analysis Set
47.5.2	Metabolic Assessments: Shift Table of Fasting Triglycerides (mg/dL) by Visit	Safety Analysis Set
47.6	Metabolic Assessments: Summary of Fasting Glucose (mg/dL) by Visit	Safety Analysis Set
47.7.1	Summary of Subjects Taking Lipid Modifying Medications at Study Entry	Safety Analysis Set
47.7.2	Summary of Subjects Initiating Lipid Modifying Medications during Double-Blind Phase	Safety Analysis Set
47.8.1	Summary of Fasting Total Cholesterol (mg/dL) at Baseline and Week 48 (Excluding Subjects Taking any Lipid Modifying Medication)	Safety Analysis Set
47.8.2	Summary of Fasting Direct LDL (mg/dL) at Baseline and Week 48 (Excluding Subjects Taking any Lipid Modifying Medication)	Safety Analysis Set
47.8.3	Summary of Fasting HDL (mg/dL) at Baseline and Week 48 (Excluding Subjects Taking any Lipid Modifying Medication)	Safety Analysis Set
47.8.4	Summary of Fasting Triglycerides (mg/dL) at Baseline and Week 48 (Excluding Subjects Taking any Lipid Modifying Medication)	Safety Analysis Set

Table Number	Title	Analysis Set

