47.8.5	Summary of Fasting Total Cholesterol to HDL Ratio at Baseline and Week 48 (Excluding Subjects Taking any Lipid Modifying Medication)	Safety Analysis Set
48.1.1	Percentage Change from Baseline in Hip Bone Mineral Density by Visit (LOCF Imputation)	Hip DXA Analysis Set
48.1.2	Percentage Change from Baseline in Hip Bone Mineral Density by Visit (Observed Data)	Hip DXA Analysis Set
48.2.1	Percentage Change from Baseline in Spine Bone Mineral Density by Visit (LOCF Imputation)	Spine DXA Analysis Set
48.2.2	Percentage Change from Baseline in Spine Bone Mineral Density by Visit (Observed Data)	Spine DXA Analysis Set
49.1	Clinical Hip Bone Mineral Density Status by Baseline Status and Visit	Hip DXA Analysis Set
49.2	Clinical Spine Bone Mineral Density Status by Baseline Status and Visit	Spine DXA Analysis Set
50.1	Gradation of the Percentage Change in Hip Bone Mineral Density by Visit	Hip DXA Analysis Set
50.2	Gradation of the Percentage Change in Spine Bone Mineral Density by Visit	Spine DXA Analysis Set
51.1	Bone Biomarkers: Summary of Serum C-type Collagen Sequence (CTX, ng/mL) by Visit	Safety Analysis Set
51.2	Bone Biomarkers: Summary of Serum Bone Procollagen Type 1 N-terminal Propeptide (P1NP, ng/mL) by Visit	Safety Analysis Set
51.3	Bone Biomarkers: Summary of Serum Parathyroid Hormone (PTH, pg/mL) by Visit	Safety Analysis Set
51.4	Bone Biomarkers: Summary of Osteocalcin (OC, ng/mL) by Visit	Safety Analysis Set
51.5	Bone Biomarkers: Summary of Bone Specific Alkaline Phosphatase (bsAP, ug/L) by Visit	Safety Analysis Set
52	Treatment-Emergent Fracture Events	Safety Analysis Set
53.1.1	Summary of 10 Year Probability of Hip Fracture (%) by Visit (Age \geq 40 Years)	Hip DXA Analysis Set
53.1.2	Summary of 10 Year Probability of Hip Fracture (%) by Visit (All Subjects)	Hip DXA Analysis Set
53.2.1	Summary of 10 Year Probability of Major Osteoporotic Fracture (%) by Visit (Age \geq 40 Years)	Hip DXA Analysis Set
53.2.2	Summary of 10 Year Probability of Major Osteoporotic Fracture (%) by Visit (All Subjects)	Hip DXA Analysis Set
54	Treatment-Emergent Bone Events	Safety Analysis Set
55	Treatment-Emergent Confirmed Renal Laboratory Abnormality	Safety Analysis Set
56.1	Summary of Serum Creatinine (mg/dL) by Visit (LOCF Imputation)	Safety Analysis Set
56.2	Summary of Serum Creatinine (mg/dL) by Visit (Observed Data)	Safety Analysis Set

Table Number	Title	Analysis Set

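### The SAP's definition of lipid modifying medication catches statins only, so tables titled as excluding users of any such drug keep subjects who take only a non-statin agent

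*SAP*

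**What the plan says.** The rule is in SAP 7.2.1, under Metabolic Assessments. "A lipid modifying medication is defined as a medication with drug class" equal to LIPID MODIFYING AGENTS "and CMDECOD containing the wording of" STATIN.

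Two sets of output use the term:

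- **Counts.** Table 47.7.1 counts subjects on lipid modifying medication at study entry. Table 47.7.2 counts those who start it during the double-blind phase.
- **Sensitivity analysis.** The SAP plans "A sensitivity analysis of fasting lipid tests (including total cholesterol, LDL, HDL, triglycerides, and total cholesterol to HDL ratio"), done by "excluding subjects who took lipid modifying medications at study entry or initiated the medications". In SAP Appendix 1 this becomes Tables 47.8.1 to 47.8.5, and all five titles carry the words "Excluding Subjects Taking any Lipid Modifying Medication".

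No other section of the SAP widens or restates the definition.

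**The concern.** The label and the rule do not match. The titles promise exclusion of users of any lipid modifying drug, while the rule removes only those whose coded drug name contains STATIN. A programmer who follows Section 7.2.1 exactly will produce output that contradicts its own titles.

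What is at stake is how the lipid safety tables are read. Someone looking at Table 47.8.4 (triglycerides) or Table 47.8.3 (HDL) would take the values to be free of lipid-drug use. They would not be, if any subject took a non-statin agent alone. Table 47.7.2, read as the number of subjects who started lipid treatment on study, would omit anyone who started only a non-statin.

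**Working it through.** No sample size, power or error rate is involved, and the plan gives no figure to reproduce. The check is to apply the rule and compare the result with the titles.

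**Step 1. Apply the two conditions.** They are joined by *and*, so both must hold.

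| Subject's lipid drugs | Class is LIPID MODIFYING AGENTS | Coded name contains STATIN | Flagged | In Tables 47.8.1 to 47.8.5 | Counted in 47.7.1 or 47.7.2 |
|---|---|---|---|---|---|
| Statin only | yes | yes | yes | removed | yes |
| Statin plus non-statin, or a combination product coded with a statin name | yes | yes | yes | removed | yes |
| Non-statin only (e.g. fenofibrate, ezetimibe) | yes | no | **no** | **kept** | **no** |
| None | no | no | no | kept | no |

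The third row is the only one where the outcome disagrees with the titles.

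**Step 2. Can such a subject be in the trial?** Protocol Section 5.4 lists the excluded medications, and Table 5-1 lists those prohibited or to be used with caution. Neither names a lipid drug. SAP 5.1 summarises hyperlipidemia at baseline and identifies it from medical history and/or concomitant medication, so the plan expects some subjects with the condition.

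**Step 3. Which outputs are affected?** Two count tables and five sensitivity tables, seven in all. The five cover total cholesterol, LDL, HDL, triglycerides and the total cholesterol to HDL ratio.

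**Step 4. How many subjects?** The documents do not say. The SAP covers about 150 China subjects (100 TAF, 50 TDF). For illustration only, assume that 5% to 10% take a lipid drug and that 10% to 40% of those take a non-statin alone. Neither range comes from the documents.

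- Low end: 150 × 0.05 × 0.10 = 0.75 subjects
- High end: 150 × 0.10 × 0.40 = 6 subjects

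That is about 1 to 6 subjects across both arms, or 0.5% (0.75/150) to 4% (6/150) of the cohort. The direction of any effect on a mean change cannot be derived, because neither the arm nor the drug of these subjects is known.

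**The case against.** The case for leaving this alone is fair on several counts.

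- **The definition is explicit and prespecified.** The SAP states no purpose for the analysis, and a class condition plus a name string could be a deliberate definition of statin use. That stands as a reason to offer retitling as an alternative. It does not rescue the titles, which say any. Nor can the rule be read as class *or* name, since the text says *and*.
- **The information is not lost.** SAP 7.8 summarises all concomitant medication by arm, drug class and preferred name. Table 65 and Listing 55 would show a fibrate or ezetimibe user, and Listing 36 gives each subject's lipids. This stands, but it leaves the seven tables mislabelled.
- **The consequence is low.** Fasting lipids appear in no listed objective or endpoint, the tables are descriptive with no between-arm test, and the main lipid tables keep all subjects whatever their medication. This stands.

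A reader might go further and infer that removing subjects who start a lipid drug on study biases the comparison, on the view that their lipids rose most. The documents do not support that: they set no criteria for starting lipid treatment and do not describe the lipid course of those who do. The obvious remedy, dropping only values taken after the start date, would not cure such a selection either. The analysis needs both a baseline and a post-baseline value at each visit, so a subject who starts before the Week 48 sample would still be missing from the Week 48 table. Only values taken before a later start would be restored.

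**Conclusion.** The mismatch between rule and titles is real and follows from the text alone. It is minor. It affects subjects on a non-statin lipid agent alone, who stay in Tables 47.8.1 to 47.8.5 and are left out of Tables 47.7.1 and 47.7.2.

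Two broader statements are tempting and should not be made. It is not true that every non-statin user is misclassified, because anyone also on a statin is flagged. It is also not established that the counts are too low: that holds only if at least one such subject exists, which the documents do not show. The illustrative 1 to 6 subjects rests wholly on assumed rates of use. No primary or key secondary result depends on this point.

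**What to change.** Preferred: in SAP 7.2.1, delete the STATIN condition and define a lipid modifying medication by drug class alone. The rule then matches the titles of all seven tables and suits the triglyceride and HDL content of the sensitivity analysis.

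Alternative, if statins only is intended: keep the rule, call it statin use in Section 7.2.1, and retitle Tables 47.7.1, 47.7.2 and 47.8.1 to 47.8.5 to match.

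The preferred change is one line of SAP text and a minor edit to the program that sets the flag. The alternative changes wording and seven titles. Neither needs new data. Whichever is chosen should be recorded in the SAP before the blind is broken for this analysis.

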7.2.2. Graded Laboratory Values

The criteria specified in the protocol will be used to grade laboratory results as Grade 0, Grade 1 (mild), Grade 2 (moderate), Grade 3 (severe) or Grade 4 (life-threatening). Grade 0 includes all values that do not meet criteria for an abnormality of at least Grade 1. Some laboratory tests have criteria for both increased and decreased levels; analysis for each direction (ie, increased, decreased) will be presented separately.

For triglycerides, LDL, and total cholesterol, the protocol-specified toxicity grade scale is for fasting test values; non-fasting lipid results (or lipid results without known fasting status) will not be graded or summarized by toxicity grades.

If any laboratory toxicity grading scale overlaps with normal reference ranges (eg, Grade 1 scale overlaps with normal reference ranges), laboratory values within normal range will not be graded except for lipid tests.

7.2.2.1. Treatment-Emergent Laboratory Abnormalities

Treatment-emergent laboratory abnormalities occurring in the double-blind phase are defined as values that increase by at least 1 toxicity grade from baseline at any postbaseline visit up to and including the last dose date of the blinded study drug (or 'last dose date of the blinded study drug + 1' for those who enter the open-label phase) for those who discontinued blinded study drug prematurely, or values that increase by at least 1 toxicity grade from baseline at any postbaseline visit for those who are still on the blinded study drug. If the relevant baseline laboratory data are missing, any laboratory abnormality of at least Grade 1 will be considered treatment-emergent.

Treatment-emergent laboratory abnormalities occurring in the open-label phase are defined as values that increase by at least 1 toxicity grade from the open-label baseline at any open-label postbaseline visit up to and including the last dose date of open-label study drug for those who discontinued open-label study drug prematurely, or values that increase by at least 1 toxicity grade from the open-label baseline at any open-label postbaseline visit for those who are still on the open-label study drug. For the analyses of abnormalities occurring during open-label treatment, baseline will be considered to be the last available record on or prior to Open-Label Study Day 1.

Fasting glucose and nonfasting glucose are graded based on different grading scales. Treatment-emergent laboratory abnormalities will be summarized for fasting glucose. Since nonfasting glucose was not assessed at baseline, the maximum postbaseline grade will be summarized.

7.2.2.2. Treatment-Emergent Marked Laboratory Abnormalities

Treatment-emergent marked laboratory abnormalities occurring in the double-blind phase are defined as values that worsen by at least 3 grades from baseline at any postbaseline visit up to and including the last dose date of the blinded study drug (or 'last dose date of the blinded study drug + 1' for those who enter the open-label phase) for those who discontinued study drug

prematurely, or values that worsen by at least 3 grades from baseline at any postbaseline visit for those who are still on blinded study drug. If relevant baseline laboratory data are missing, any laboratory abnormalities of at least Grade 3 or 4 will be considered as treatment-emergent marked laboratory abnormalities.

Treatment-emergent marked laboratory abnormalities occurring in the open-label phase are defined as values that worsen by at least 3 grades from the open-label baseline at any open-label postbaseline visit up to and including the last dose date of open-label study drug for those who discontinued open-label study drug prematurely, or values that worsen by at least 3 grades from the open-label baseline at any open-label postbaseline visit for those who are still on open-label study drug.

